# 7.7.3 Poolability and Homogeneity of Treatment Effects

The primary analysis will be based on the ITT analysis set and will use multiple imputation to address missing values. The MI model will include sphere, cylinder, and axis measurements for both the investigational device and the gold standard device and baseline characteristics including age and gender. Analyses will be repeated in a per protocol analysis set that includes eyes will complete data. A tipping point analysis will be performed to evaluate the robustness of results with regard to the missing-at-random (MAR) assumption necessary for the validity of the MI analyses.

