# 4.9.5 Subject Discontinuation or Withdrawal

Subjects may withdraw their consent to participate in the clinical study at any time, for any reason. In addition, it may be necessary to terminate a subject from the clinical study due to medical safety consideration, non-compliance, or administrative concerns. If for any reason a subject is withdrawn or terminated before completing the study, the reasons for withdrawal or termination must be documented. If a subject is withdrawn or terminated due to medical safety considerations because of an adverse event, the adverse event must be followed by medical attention to satisfactory resolution and all study data related to the subject will be reported.

Subjects who withdraw or are withdrawn prior to completion of the study periods will be scheduled a termination visit. At this visit, all study procedures will be completed according to the next

scheduled visit per protocol. All pertinent data will be documented in the source documents and the CRFs including a Study Exit form

If the site is notified that a subject plans to withdraw during a study visit, the site will treat the current visit like the termination visit by completing the current visit (if able), all applicable source documents and the CRFs including the Study Exit CRF.

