# 5.0 Safety Evaluation

Adverse events are defined as any untoward medical occurrence, unintended disease or injury, or untoward clinical signs (including abnormal laboratory findings) in subjects, users, or other persons, whether or not related to the investigational medical device. See section 8.0 for anticipated risks during the trial.

All adverse events will be collected and recorded, regardless of whether or not they are believed to be related to the device or anticipated. This includes the following:

- Adverse Device Effect (ADE) adverse event related to the use of an investigational medical device.
- Serious Adverse Events (SAE) an adverse event that led to death; led to serious deterioration in the health of the subject, that either resulted in: a life-threatening illness or injury; a permanent impairment of a body structure or a body function; in-patient or prolonged hospitalization; medical or surgical intervention to prevent life-threatening

illness or injury or permanent impairment to a body structure or a body function; led to fetal distress, fetal death or congenital abnormality/birth defect.

- Unanticipated Adverse Device Effect (UADE) any serious adverse effect on health or safety or any life-threatening problem or death caused by, or associated with, a device, if that effect, problem, or death was not previously identified in nature, severity, or degree of incidence in the investigational plan or application (including a supplementary plan or application), or any other unanticipated serious problem associated with a device that relates to the rights, safety, or welfare of subjects.
- Device deficiency inadequacy of a medical device with respect to its identity, quality, durability, reliability, safety or performance.

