#### 7.2.3 Per Protocol

Primary effectiveness analyses may be repeated in a Per Protocol (PP) analysis set. The PP analysis set will exclude from the ITT analysis set patients that had clinically significant violations of inclusion or exclusion criteria or post randomization protocol violations that may reasonably be predicted to impact on effectiveness endpoints and those that have missing data.

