# 7.4 Primary Effectiveness Hypothesis

The primary hypothesis for this study is that the probability of simultaneously achieving good clinical agreement for sphere, cylinder, and axis exceeds a performance goal for measurements made by the LFR-260 compared to those obtained using the control device, *traditional phoropter*.

Symbolically, the null and alternative effectiveness hypotheses are: :

Ho:  $\pi \le PG$ Ha:  $\pi > PG$ 

Where  $\pi$  is the true probability that the LFR 260 is within 0.5D (+/-) in measuring sphere and cylinder results and within 10 degrees for axis results among subjects with low astigmatism and within 5 degrees among subjects with moderate to high astigmatism from the traditional phoropter.

For this study, PG is set to 0.80.

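### Eyes with no LFR-260 result for a device-related reason are imputed in the primary analysis and dropped from per protocol, so neither analysis counts them as failures

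*Combined protocol and SAP*

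**What the plan says.** The hypothesis in 7.4 is that "the probability of simultaneously achieving good clinical agreement for sphere, cylinder, and axis exceeds a performance goal" of 0.80. The sentence goes on to refer to measurements made by the LFR-260 compared with the control device. Section 7.6 declares success if the one-sided exact binomial lower bound exceeds 0.80.

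For missing data, 7.7.3 says: "The primary analysis will be based on the ITT analysis set and will use multiple imputation to address missing values". The synopsis (Statistical Considerations) gives the same rule. On the model, 7.7.3 says: "The MI model will include sphere, cylinder, and axis measurements for both the investigational device and the gold standard device and baseline characteristics including age". Gender is also named. The reason for missingness is not among the listed variables. The section adds: "A tipping point analysis will be performed to evaluate the robustness of results with regard to the missing-at-random (MAR) assumption". It states no range, direction, worst case or consequence for the success rule.

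The per-protocol set in 7.2.3 excludes, among others, "those that have missing data".

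Elsewhere the protocol recognises events that could leave an eye without an LFR-260 result. Section 5.0 collects device deficiencies, defined as "inadequacy of a medical device with respect to its identity, quality, durability, reliability, safety or performance". Section 4.9.5 allows the study to "terminate a subject from the clinical study due to medical safety consideration, non-compliance, or administrative concerns" and requires the reason to be documented. Nothing links these records to the primary endpoint, and neither 7.3 nor 7.4 says how an eye with no obtainable LFR-260 result is classified.

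**The concern.** Multiple imputation under missing-at-random suits a value that exists in principle but was not recorded. It does not suit an eye for which the device could not produce a value. For such an eye the model supplies a hypothetical LFR-260 reading, based on how the device behaved in the eyes it did measure and on that eye's own phoropter reading. The eye is then scored against the agreement limits as though the device had worked.

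The per-protocol analysis is no counterweight, because it removes the same eyes. Both planned effectiveness analyses then estimate agreement among eyes the LFR-260 can measure, and the ITT version reports this as agreement in all randomised eyes. For device-caused missingness the bias runs one way, towards passing. The single primary pass/fail decision is at stake.

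**Working it through.** **Inputs from the plan.** Performance goal 0.80 (7.4). Assumed true agreement 0.90, one-sided exact binomial test at alpha 0.05, 216 eyes, stated power 99% (7.5). Success if the exact lower bound exceeds 0.80 (7.6).

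**Assumption.** Let f be the share of eyes with no LFR-260 result for a device-related reason. The documents give no value, so a range is shown. Let q be the agreement rate among measured eyes. Eyes are treated as independent, as in 7.5.

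**Step 1: the plan's own figure.** The smallest passing count is 183/216 (84.7%), with one-sided 95% Clopper-Pearson lower bound 0.801; 182/216 gives 0.796. P(X ≥ 183 | n = 216, p = 0.80) = 0.0461 and P(X ≥ 183 | n = 216, p = 0.90) = 0.9946. The stated 99% power is reproduced.

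**Step 2: chance of a false pass.** Define the true probability so that non-results count as failures, and set it at the null: q(1 − f) = 0.80, so q = 0.80/(1 − f). Imputing at rate q adds no information beyond the measured eyes, so the imputed analysis is approximated by the exact test on the n = 216(1 − f) measured eyes. This is also the complete-case calculation.

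| f (assumed) | measured eyes | passing count | q | chance of passing |
|---|---|---|---|---|
| 0% | 216 | 183 | 0.800 | 4.6% |
| 2% | 212 | 180 | 0.816 | 12.5% |
| 3% | 210 | 178 | 0.825 | 22.0% |
| 5% | 205 | 174 | 0.842 | 44.2% |

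A simulation of 200,000 trials, with the number of missing eyes varying at random, gave 12.5% to 14.3% at f = 2% and 42.5% to 46.8% at f = 5%. The lower figure is the complete-case test and the upper a single randomly completed data set. With non-results scored as not in agreement, the chance stayed at about 4.6%.

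**Step 3: a worked case.** Suppose 10 eyes have no LFR-260 result for device reasons and 177 of the 206 measured eyes agree (85.9%).
- Imputed: expected total 177 + 10 × 177/206 = 185.6 of 216, above 183.
- Complete data: 177/206, lower bound 0.813, a pass.
- Scored as not in agreement: 177/216 = 81.9%, lower bound 0.771, a fail.

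**Step 4: how many such eyes reverse a pass.** Find the smallest m for which q(216 − m), rounded, is below 183.
- q = 0.90: 0.90 × 202 = 181.8, so 182; m = 14 (6.5%).
- q = 0.88: 0.88 × 207 = 182.2, so 182; m = 9 (4.2%).
- q = 0.86: 0.86 × 212 = 182.3, so 182; m = 4 (1.9%).

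In each case 182/216 has lower bound 0.796 and fails.

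**Step 5: power if such eyes are scored as failures.** P(X ≥ 183 | n = 216, p = 0.90(1 − f)) is 99.5% at f = 0, 95.0% at 2%, 67.0% at 5% and 9.3% at 10%.

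**The case against.** Several counter-arguments carry weight.

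*Missingness may be negligible.* A reader might infer that LFR-260 results will often be absent. The documents do not support that. Subjects are healthy volunteers with a long list of ocular exclusions, there is one visit (4.10), and the tests are non-invasive and described as minimal risk (8.0). The device-deficiency wording in 5.0 is a general safety definition, and nausea is mentioned only for a head-injury subgroup, if applicable (4.11). Section 4.9.5 also asks for procedures to be completed at a termination visit or, if able, at the current visit. This stands: the frequency is unknown and could be zero.

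*The target quantity is ambiguous.* The 7.4 wording about measurements made by the LFR-260 could be read as conditional on a measurement existing. The symbolic definition of π does not state that condition. This stands in part: scoring non-results as failures is a choice of estimand, and the false-pass rates in step 2 depend on it. The plan does not make the choice explicitly; its blanket imputation rule makes it by default.

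*The bias is not universal.* It is tempting to say that failures are always turned into successes, or that any missing eye favours the device. Neither is right. Imputation draws on all measured eyes, including those that disagree, so credit is given at about the observed rate. For administrative or unrelated loss, imputation is not an error. Nor do the documents suggest that an examiner would stop poor LFR-260 sessions to gain from the rule.

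*A sensitivity analysis is planned.* The tipping-point analysis could show that a pass is fragile, and per protocol is only supportive. But success is fixed by 7.6 alone, and the tipping-point analysis has no stated worst case or decision role.

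*The worked case lies near the threshold.* True: at the planned 90%, reversal takes about 14 eyes rather than a handful.

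**Conclusion.** The concern holds for device-related non-results. The plan states one imputation rule for all missing values and removes incomplete data from per protocol, so an eye the LFR-260 could not refract never counts as a failure in either analysis. That can produce a pass that would not occur if such eyes were scored as not in agreement.

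The size depends on an unknown rate: no effect if every eye is measured, and a false-pass chance rising from 4.6% to about 12.5%, 22% and 44% at assumed rates of 2%, 3% and 5%. These figures assume that non-results count as failures, that the true probability is exactly 0.80, and that eyes are independent. They are not forecasts of what this trial will show.

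This should be fixed. It does not make the primary analysis invalid as it stands, because the documents give no sign that device failures will be common and the wording of the hypothesis leaves room for a conditional reading. The rule should be set before data are seen, since afterwards the choice could itself decide pass or fail.

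**What to change.** - In 7.4, 7.7.3 and the synopsis, state that a randomised eye with no LFR-260 refraction for a documented device-related reason (device deficiency, intolerance or device-related adverse event, or no end-point reachable) is scored as not in agreement in the primary ITT analysis.
- Limit multiple imputation to reasons unrelated to the LFR-260, such as an administrative stop, a missing phoropter reading, or a subject leaving before the LFR-260 session.
- Amend 7.2.3 and the matching sentences in 7.7.3 and the synopsis so that a device-related non-result is not removed from per protocol merely because data are missing.
- Record the reason for each missing refraction by eye and by device, for example on the Study Exit Form, and report the number of such eyes.
- Include in the tipping-point analysis the case in which all eyes missing an LFR-260 result fail.

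The cost is wording and one reason field, with no extra subjects or procedures. The real downside is a lower observed agreement rate, and lower power, if device failures occur: at 90% measured-eye agreement, power falls from 99.5% to 95% with 2% such eyes and to 67% with 5%. The sponsor should accept that trade knowingly.

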# 7.7.4 Reliability and Repeatability Analysis

Reliability of LFR-260 will be conducted in a subset of subjects for which measurements will be obtained twice in an office context. This analysis will be repeated in a remote context. Reliability will be evaluated using intraclass correlations for each of the continuous measurements, sphere, cylinder, and axis and for the vector measurement of sphere and cylinder.

For a subset of 33 subjects (66 eyes), the LFR-260 device will be measured again approximately 60 minutes after the initial assessment in order to measure the repeatability/accuracy of the device.

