The primary analysis will be based on the intent-to-treat (ITT) analysis set and will use multiple imputation to address missing values. The multiple imputation (MI) model will include sphere, cylinder, and axis measurements for both the investigational device and the gold standard device and baseline characteristics including age and gender. Analyses will be repeated in a per protocol analysis set that includes eyes with complete data.

Reliability (repeatability and reproducibility) of LFR-260 will be conducted in a subset of subjects for which measurements will be obtained twice in an office context. This analysis will be repeated in a remote context. Reliability will be evaluated using intraclass correlations for each of the continuous measurements, sphere, cylinder, and axis.

.

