# 1.2 Device Name and Intended Use

The LFR-260 is intended to be used for distance vision testing in any environment, may it be in optometric clinics or in the field outside of the clinic, because of its compact form factor and portability.

The LFR-260 is an application-controlled instrument providing capabilities for distance vision testing including sphere, cylinder, and axis. The visual acuity and eye subjective manifest refraction determination will always be administered by an eye care professional (ECP) licensed and registered by the appropriated body in the region intended to be used. The instrument is designed in a way that it will only work with approved personnel and the use of secure credentials.

The device is intended to be used in patients aged from 12-65 years old with healthy visual systems and a refractive error no bigger than (+10 to -15D) and astigmatism no bigger than 2.5D (if any).

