# 4.9.3 Offsite Testing

In a separate subset of 21 patients (7 per location), LFR-260 testing will be completed by the ECP operators offsite at each location.

After the initial LFR-260 and traditional phoropter is complete within the clinic, participants in the offsite testing cohort will be taken to a non-clinical setting for the following procedure:

- 1. An additional LFR-260 will be set up in a remote location (room separate from clinic).
- 2. The patient will be taken to the remote room, and the ECP will perform the refraction.
- 3. Best Corrected Visual Acuity will be measured and collected.
  - a. Results will be captured to compare against the initial LFR-260 refraction results.

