# 4.9.4 Remote Testing

In a separate subset of 21 patients (7 per location), LFR-260 testing will be completed by the ECP operators remotely at each location.

After the initial LFR-260 and traditional phoropter is complete, participants in the remote testing cohort will remain in the clinical setting for the following procedure, while the ECP relocates to an area outside of the exam room:

- 1. The patient will be shown the LFR-260 and site staff will oversee the telehealth refraction remotely on the LFR-260 by the ECP.
- 2. Results for the Best Corrected Visual Acuity will be collected.
  - a. Results will be captured to compare against the initial LFR-260 refraction results.

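### The remote reliability analysis in section 7.7.4 does not match the single remote reading taken, and the extra offsite reading has no named statistic; paired signed differences would suit both

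*Combined protocol and SAP*

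**What the plan says.** The reliability plan is in section 7.7.4, with a shorter version in the synopsis under Statistical Considerations. It rests on a subset in which "measurements will be obtained twice in an office context", and then states: "This analysis will be repeated in a remote context". The statistic is given as: "Reliability will be evaluated using intraclass correlations for each of the continuous measurements, sphere, cylinder, and axis"; section 7.7.4 adds the sphere-cylinder vector. It names no ICC form, confidence interval or acceptance limit. The synopsis spells out what reliability covers: "Reliability (repeatability and reproducibility) of LFR-260 will be conducted in a subset of subjects for which measurements will be obtained twice in an office context".

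The testing schedule is in section 4.9 and the study flowchart. On remote testing, section 4.9.4 says: "In a separate subset of 21 patients (7 per location), LFR-260 testing will be completed by the ECP operators remotely at each location". The flowchart shows one remote refraction, and its purpose is stated: "Results will be captured to compare against the initial LFR-260 refraction results". On offsite testing, section 4.9.3 says: "In a separate subset of 21 patients (7 per location), LFR-260 testing will be completed by the ECP operators offsite at each location". It states the same comparison with the initial LFR-260 result.

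Section 1.2 sets the ambition that these two subsets serve: "The LFR-260 is intended to be used for distance vision testing in any environment".

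**The concern.** The analysis text and the schedule describe different data. The office analysis uses two readings taken in the same setting. Remote subjects have one reading in clinic and one remote, so the same analysis cannot be run on them. If an ICC is computed on the in-clinic and remote pair and reported under the reliability heading, it will be labelled as something it does not measure.

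The main risk in moving the device or the eye care professional (ECP) is a systematic shift in the refraction. An ICC scales error by the spread between subjects, and eligibility allows spherical equivalents from +10 to -15. A sphere ICC may therefore look excellent while a clinically relevant shift goes unremarked. The additional offsite reading is the only one taken in a non-clinical setting, and section 7 names no statistic for it. At stake is the planned evidence for use away from the ordinary exam-room arrangement.

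**Working it through.** **The plan's own figure.** The only power figure in the documents is the 99% in section 7.5. With 216 eyes, a goal of 0.80 and one-sided alpha 0.05, the exact binomial rule is at least 183 successes (exact alpha 0.0461). Power at a true rate of 0.90 is 0.9946, so the figure reproduces, with eyes treated as independent. It does not depend on the remote or offsite readings.

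**LFR-260 readings per subject** (sections 4.9.2 to 4.9.4 and the flowchart)

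| Subset | Subjects | Readings |
|---|---|---|
| Repeatability | 33 | 2 in clinic, same ECP, about 1 hour apart |
| Reproducibility | 33 | 2 in clinic, two ECPs |
| Offsite | 21 | 1 in clinic, 1 offsite |
| Remote | 21 | 1 in clinic, 1 remote |

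The subsets sum to 33 + 33 + 21 + 21 = 108, the whole sample. No subject has two remote or two offsite readings.

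**What the remote context covers.** Section 4.9.3 describes the offsite room as a remote location. The note at the end of section 4.9.1 refers to Remote Testing but cites 4.9.2 and 4.9.3, and 4.9.3 is Offsite Testing. The phrase in 7.7.4 could mean section 4.9.4, section 4.9.3 or both.

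**How an ICC reacts to a setting shift.** The documents give no variances, so these are assumptions: within-eye SD sw = 0.25 D, between-subject SD sb from 1 to 3 D, shift d from 0 to 0.75 D.

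- Absolute-agreement ICC = sb² / (sb² + d²/2 + sw²)
- Consistency ICC = sb² / (sb² + sw²), unaffected by d
- SD of the paired difference = sw × √2 = 0.354 D
- Share within 0.5 D = Φ((0.5 − d)/0.354) − Φ((−0.5 − d)/0.354)

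Example, sb = 2 and d = 0.5: 4 / (4 + 0.125 + 0.0625) = 0.955. The share is Φ(0) − Φ(−2.83) = 0.498.

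| Shift d | Absolute ICC, sb = 1 | sb = 2 | sb = 3 | Eyes within 0.5 D |
|---|---|---|---|---|
| 0 | 0.94 | 0.985 | 0.993 | 84% |
| 0.25 D | 0.91 | 0.977 | 0.990 | 74% |
| 0.50 D | 0.84 | 0.955 | 0.980 | 50% |
| 0.75 D | 0.74 | 0.921 | 0.963 | 24% |

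The consistency ICC stays at the first-row values (0.94, 0.985, 0.993) whatever the shift. For a narrower range, as is likely for cylinder (capped at 2.5 D by the inclusion criteria), the absolute ICC reacts more: at sb = 0.6 D it falls from 0.36/0.4225 = 0.85 with no shift to 0.36/0.5475 = 0.66 with a 0.5 D shift.

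**Precision of paired differences in one subset.** Assume 42 eyes, difference SD 0.354 D and design effect 1.5, that is, a within-subject correlation of 0.5 between the two eyes' differences.

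- Mean shift: 1.96 × 0.354 × √(1.5/42) = ±0.13 D
- Each limit of agreement: 1.71 × 0.131 = ±0.22 D, where 1.71 = √(1 + 1.96²/2)

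For between-eye correlations from 0 to 1 the design effect runs from 1 to 2, giving ±0.11 to ±0.15 D for the mean and ±0.18 to ±0.26 D for each limit.

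**The case against.** The strongest defence is that two remote readings are needed only on one reading of one sentence. Sections 4.9.3 and 4.9.4 both state the pair to be compared, and an ICC on that pair can be computed without new data. That is correct. But such an ICC is agreement between settings, whereas the synopsis defines reliability as repeatability and reproducibility.

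A reader might infer that the offsite subjects are left out of the statistical plan. The documents do not support that: all randomized subjects are in the ITT set, so these subjects contribute to the primary and Bland-Altman analyses. The protocol's loose use of the word remote may also bring the offsite reading under the 7.7.4 sentence. What remains is an undefined term and no named statistic for the additional reading.

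A reader might also infer that use outside the clinic goes untested. That is too strong. In 42 of 108 subjects the device is read with the patient offsite or the ECP remote, against a stated comparator. What is missing is a suitable method and a criterion.

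It is fair to add that the insensitivity of the ICC depends on the measurement. It is marked for wide-range sphere and for any consistency ICC, and weaker for cylinder. The plan does not commit to the consistency form, though it does not exclude it.

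Finally, the repeatability subset might seem a ready control for the passage of time. The documents do not support using it so: its repeat is at about one hour by the same ECP, while sections 4.9.3 and 4.9.4 state neither the repeat interval nor that the same ECP repeats the test.

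**Conclusion.** The concern holds in limited form. The remote sentence in 7.7.4 either cannot be carried out as written or would report between-setting agreement as reliability. The term remote context is undefined, and the additional offsite reading has no named statistic.

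This is more than missing detail, because the named statistic suits the stated comparison poorly. Under the assumed within-eye SD of 0.25 D, a sphere shift that leaves only half the eyes within 0.5 D can coexist with an ICC of 0.955 or higher once the between-subject SD is 2 D or more. Those SDs, the shift and the design effect are assumptions; the mismatch between plan and schedule rests on the documents alone.

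The point concerns supporting analyses. The primary hypothesis, its test and its power are unaffected.

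**What to change.** In section 7.7.4, and to match in the synopsis, replace the remote sentence with text to this effect:

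- For the remote subset (n = 21) and the offsite subset (n = 21) separately, analyse the signed difference between the additional LFR-260 reading and the same subject's initial in-clinic LFR-260 reading, for sphere, cylinder and axis.
- Report the mean difference with a 95% CI clustered by subject, the limits of agreement, and the proportion of eyes within the tolerances of the primary endpoint.
- Apply the term reliability, and the ICCs, only to the repeatability and reproducibility subsets.
- The same differences in the repeatability subset may be shown as descriptive context only, with the repeat interval and the ECP reported for every subset. They cannot separate setting from time or operator.

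Use the words remote and offsite consistently across sections 4.9 and 7.7.4, and correct the cross-reference in section 4.9.1. The cost is SAP wording and a few more tables. No extra visit or reading is needed, though the repeat interval and the ECP must be recorded.
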